2.5 Study design

For Aim 1, we will adapt a couple-based MI framework and interventions developed by co-I [name] (*We Test* and the *Couples Health Project*) to address alcohol use in heavy alcohol users and their primary partners and incorporate the mobile breathalyzer component. We will follow the ADAPT-ITT framework by conducting focus group discussions (FGDs) with around 40 key stakeholders to gain feedback on the intervention and then refining the intervention. For Aim 2, we will develop training procedures, study procedures, and data collection instruments that will be pilot tested during the RCT. For Aim 3, we will conduct a three-arm RCT with 30 couples randomized to the following arms (90 couples total): 1) an enhanced usual care control condition; 2) couple-based MI; and 3) couple-based MI with mobile breathalyzers for real-time feedback. For arm 2 and 3, couples will receive 3 MI sessions over a 60-day period with an experienced counselor to help strengthen communication and problem-solving skills around alcohol use. For Arm 3, couples will use the mobile breathalyzers and app for 60 days and receive the same MI sessions, which will also incorporate feedback on BAC levels (prior 30 days) and teach couples how to effectively engage with the breathalyzers. This design will allow us to assess the effectiveness of couple-based MI alone and the added synergistic effect of the mobile breathalyzers on alcohol use and HIV outcomes (e.g., adherence to antiretroviral therapy (ART), viral suppression). Our F&A outcomes will include enrollment and retention rates, satisfaction with both intervention arms, MI session attendance rates, and follow-up survey completion rates. We will also conduct qualitative interviews with a subset of 15 couples to contextualize F&A data and refine the intervention and procedures for a future full-scale efficacy trial.

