5.7 Recruitment and retention. We will recruit and randomize around 120 couples to meet our target sample size of 90 couples, assuming that we will lose around 25-30% of couples after randomization. We anticipate that we will lose a very small percentage of couples due to break-ups, deaths, and migration (<5% in Uthando Lwethu), which we have accounted for in recruitment and analysis plans.

5.8 Randomization process. After informed consent and the baseline assessment, couples will be randomized to either the control arm, the couple-based MI arm, or the couple-based MI with

Couple-Based Motivational Interviewing with Mobile Breathalyzers to Reduce Alcohol Use in South Africa

mobile breathalyzers arm (MI *Plus*). We will use randomly permuted block sizes (e.g., 3, 6, and 9) generated using a computerized and secure process. The UCSF project coordinator and the HSRC data manager will use the table that the statistician created to print documents that assign participants to one of the three arms. These documents will be placed in sealed envelopes and maintained by the HSRC data manager. HSRC interviewers will take a small subset of envelopes into the field with them. At the end of the baseline survey, the index patient will be given the envelope that contains the random assignment. Couples will receive an appointment card with a date for their next study visit following randomization.

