5.14 Exit interviews

Sampling: To contextualize the feasibility and acceptability data, we will conduct 60-90 minute exit interviews with 15 couples at the 2-month follow-up. Around five couples will be recruited from each arm, purposively sampled by participation level. For Arm 2, participation will be categorized as: low=attended one MI session, medium=attended two sessions, and high=attended all three sessions. For Arm 3, we will aim to enroll couples with varying test completion rates, categorized as low=completed less than 70% of breathalyzer tests, medium=completed 70-85% of tests, and high=completed>85% of tests. We will also try to interview couples in which both partners were heavy alcohol users to further understand how the intervention impacts dual drinkers.

Interview questions: We will elicit information on intervention preferences and satisfaction with domains of the intervention (e.g., frequency of breathalyzer tests and MI sessions, length, content, format of MI sessions). To explore dyadic mechanisms of change, we will elicit information on whether and how the breathalyzers and MI sessions enhanced communication, communal coping, and support. We will also elicit information on technology issues (e.g., user app experience, network connectivity, load shedding and power outages, battery life, trouble with logins) and contextual issues (e.g., literacy, alcohol stigma). Given the central question of whether the mobile breathalyzer technology can be used with couples to trigger support, we will assess how knowledge of BAC levels impacts the relationship (e.g., increases in couple conflict, changes in communication), how both partners interpret and respond to BAC levels, and the types of partner support provided and when.

Couple-Based Motivational Interviewing with Mobile Breathalyzers to Reduce Alcohol Use in South Africa

Procedures: Given the gender-power dynamics in this setting, the PI [name]'s prior qualitative research, and the potential bias (e.g., women not feeling comfortable voicing their opinions in front of male partners) and increased risk for violence that could result from interviewing partners together, we will interview both partners separately, but simultaneously. Interviews will be audio-recorded, transcribed word-for-word, and translated from *isiZulu* to English, and imported into Dedoose for analysis.

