7.0 STATISTICAL CONSIDERATIONS

7.1 Analysis of FGDs to refine the intervention. Using a template analysis approach [50], we will develop a pre-determined template based on elements of the intervention to retain or refine, and new elements to add to address the needs of the target population. Study investigators will generate a draft of the template with thematic codes for relevant domains of the intervention, and will independently code the FGD transcripts. The investigative team will then discuss the emerging themes, identify areas for further adaptation, and refine the intervention manual. Depending on the extent of the changes, we may hold a meeting with HSRC's CAB to review

Couple-Based Motivational Interviewing with Mobile Breathalyzers to Reduce Alcohol Use in South Africa

the FGD findings and identify intervention content and procedures that need to be added, removed, or refined.

7.2 Feasibility and acceptability data analysis. Our primary objective is to evaluate F&A of the intervention and study procedures. The primary analyses will include descriptive statistics of F&A indicators, comparing each statistic (e.g., percent retained) to the threshold listed in Table 4. Above-threshold findings will suggest a reasonable level of F&A while below-threshold findings would suggest that remedial modifications to study procedures and/or design would be required prior to moving forward with a full-scale trial. We will stratify the statistics by gender to consider sex as a biological variable.

Couple-Based Motivational Interviewing with Mobile Breathalyzers to Reduce Alcohol Use in South Africa

Table 4. F&A Domain	Measure	Threshold	Arm(s)
Recruitment	Number of couples enrolled per week	Average 5 per week/20 per month	All
Enrollment	Proportion of eligible couples who enroll and complete baseline assessment	80% of eligible couples will complete enrollment	All
Randomization	Proportion of enrolled couples who complete randomization process	90% of enrolled couples will complete randomization	All
Participation	Proportion of couples who attend 66% and 100% of MI sessions	100% of couples will attend 66% (2 out of 3) of sessions; 75% of couples will attend all 3 sessions	2, 3

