Engagement with mobile breathalyzer technology	Proportion of breathalyzer tests taken after prompted; number of partner SMS messages sent and received on BAC results; number of drinker SMS reminders to take breathalyzer tests sent and received; average length of time to take breathalyzer tests after prompted; average number of app logins per week to access BAC data (for both partners); average user session length; number of lost/stolen phones and breathalyzers	70% completion rate	3
Retention	Retention rates; reasons for dropouts	85% retention at 2-month follow-up	All
Process outcomes	Length of MI sessions in minutes	≤90 minutes per session[9]	2, 3
Intervention fidelity	Expert ratings of quality of intervention using audio-recorded intervention sessions (checklists)	>80% inter-rater reliability	2, 3
Assessment procedures	Length of surveys; proportion of couples who complete baseline, 1, 2, and 6-month surveys	90 minutes; 75% of all couples will complete all assessments	All

Couple-Based Motivational Interviewing with Mobile Breathalyzers to Reduce Alcohol Use in South Africa

Acceptability	Proportion of couples satisfied with the intervention. Couples will decide their satisfaction together since this is a dyadic intervention.	75% of couples reporting being satisfied or very satisfied	All
---------------	---	--	-----

Couple-Based Motivational Interviewing with Mobile Breathalyzers to Reduce Alcohol Use in South Africa

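### Table 4 asks that every couple in arms 2 and 3 attend at least 2 of 3 MI sessions, so one counted couple below that misses the threshold, although the plan provides for such couples

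*Combined protocol and SAP*

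**What the plan says.** Section 7.2 makes the primary analysis a set of descriptive feasibility and acceptability statistics, "comparing each statistic (e.g., percent retained) to the threshold listed in Table 4". On the consequence of a shortfall it says "below-threshold findings would suggest that remedial modifications to study procedures and/or design would be required prior to moving forward with a full-scale trial".

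The Participation row of Table 4 applies to arms 2 and 3 and has two elements: "100% of couples will attend 66% (2 out of 3) of sessions; 75% of couples will attend all 3 sessions". The row gives no tolerance, no confidence interval and no denominator (all randomised couples, couples who started, or couples retained). Nothing says which element governs if one is met and the other is not.

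Other parts of the plan bear on whether couples will fall below 2 of 3:

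- Section 5.14 sorts Arm 2 couples for exit interviews as "low=attended one MI session, medium=attended two sessions, and high=attended all three sessions".
- Section 5.7 states: "We will recruit and randomize around 120 couples to meet our target sample size of 90 couples". Sections 3.2 and 5.7 put the loss after randomization at 25-30%.
- Section 3.3 has couples who separate before taking part in the intervention leave the study. Section 5.8 randomizes at the end of the baseline survey and section 4.0 allows up to two weeks until session 1, so a randomised couple can have no sessions.
- The Retention row of Table 4, for all arms, is "85% retention at 2-month follow-up".

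**The concern.** A threshold of 100%, compared with an observed proportion, has no room for a single exception. The Arm 2 low stratum in section 5.14 consists of couples who attended one session. If one such couple is found and counted, the 2-of-3 element has already been missed. The recruitment assumptions and the exit rule for couples who separate add further routes to no session or one session.

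This matters because the Table 4 comparison is the pilot's primary analysis. If the 2-of-3 element falls short under very good attendance as well as poor attendance, its result says little about whether the MI sessions are feasible. The team would then either report a shortfall that does not reflect a real problem, or set aside a pre-stated threshold after seeing the data.

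**Working it through.** **Inputs.** Planned size is 30 couples per arm (section 2.5), so 2 × 30 = 60 in arms 2 and 3. About 120 couples are to be randomised (section 5.7); with equal allocation that is 2 × 40 = 80 in arms 2 and 3. The denominator is not stated, so both are used. The true probability p that a couple attends at least 2 sessions is not given and is varied. Couples are assumed to attend independently of one another.

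**The plan's own related figure.** The documents give no operating characteristics for this row. The one related figure that can be checked is the recruitment number: 90 / (1 − 0.25) = 120, which reproduces the plan's figure. At 30% loss, 90 / (1 − 0.30) = 128.6, so 129 would be needed. Equivalently, 120 × 0.75 = 90 and 120 × 0.70 = 84.

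**One exception.** 59/60 = 98.3% and 79/80 = 98.75%. Both are below 100%.

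**Chance of meeting the 100% element.** All n couples must attend at least 2 sessions, so P(met) = pⁿ.

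| True p | n = 60 | n = 80 |
|---|---|---|
| 0.99 | 0.547 | 0.448 |
| 0.98 | 0.298 | 0.199 |
| 0.95 | 0.046 | 0.017 |
| 0.90 | 0.0018 | 0.0002 |

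For an 80% chance of meeting it, p must be 0.80^(1/60) = 0.996 with 60 couples, or 0.80^(1/80) = 0.997 with 80.

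**The other element of the row.** The 75% all-sessions element needs 0.75 × 60 = 45 couples. The binomial probability of 45 or more out of 60 is 0.011, 0.244, 0.569, 0.869 and 0.9998 when the true all-sessions rate is 60%, 70%, 75%, 80% and 90%. This element separates poor from good attendance.

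**Assumed loss.** A loss of 25-30% is 15 to 18 of 60 couples, or 20 to 24 of 80. The documents do not say how many of those couples would have attended fewer than 2 sessions.

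**Illustrative lower thresholds for 2 of 3 sessions, n = 60.**

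| Threshold | p = 0.75 | p = 0.80 | p = 0.85 | p = 0.90 | p = 0.95 |
|---|---|---|---|---|---|
| 80% (48/60) | 0.232 | 0.576 | 0.894 | 0.994 | 1.000 |
| 85% (51/60) | 0.045 | 0.213 | 0.588 | 0.927 | 0.999 |
| 90% (54/60) | 0.003 | 0.031 | 0.185 | 0.606 | 0.970 |

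**Why the denominator matters.** Suppose all of the assumed loss fell before session 2 and all randomised couples were counted. True attendance would then be at most 70-75%, and an 85% threshold (68 of 80) would be met with probability of only 0.002 to 0.022. A lower number without a stated denominator would therefore not settle the matter.

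**The case against.** The strongest reply is that section 7.2 is descriptive and hedged. It states no stop/go rule, both proportions will be reported, and they will be read alongside exit interviews and team discussion. This stands: missing the element does not halt anything. It does not explain why this cell sits among thresholds that all carry the same stated consequence, with nothing marking it as a goal only.

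A reader might infer from the 85% retention row that the plan contradicts itself, since it accepts 15% loss by month 2 and yet demands full attendance. The documents do not support that. Session 2 falls at about 30 days (section 4.0), so a couple lost by month 2 may already have attended twice. A couple who skipped sessions can still be retained, because follow-up surveys may be done by phone (section 5.11). The retention row allows for non-attending couples without implying them. Nor does any other Table 4 row set an MI attendance level that could be said to accept what this one rejects.

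A reader might also conclude that the Participation row as a whole cannot tell feasible from infeasible. That goes too far, because the 75% all-sessions element can.

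Two limits also stand. Section 5.14 defines sampling categories in Arm 2 only, whereas Arm 3 is stratified by breathalyzer completion. Defining a low category provides for such couples but does not forecast them. And if only couples who started or stayed were counted, much of the assumed loss would not enter the calculation, though the Arm 2 stratum would still conflict. Finally, the attendance data cited in section 2.1 are favourable: 19 of 20 couples completed all three sessions in an earlier pilot in a different population. The number attending at least two is not given there.

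**Conclusion.** The point holds for the 2-of-3 element of the Participation row. A literal 100% threshold is missed by one counted couple with no session or one session, the plan provides for such couples in sections 3.2, 3.3, 5.7 and 5.14, and no passage reconciles them.

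With independent attendance, the element is missed about 70% of the time at a true rate of 98% and about 95% of the time at 95% with 60 couples (80% and 98% with 80 couples). At 99% it is close to an even chance either way. It would therefore usually point towards modification even with very good attendance. These figures rest on assumed attendance rates, on independence between couples, and on a denominator of 60 or 80 that the plan does not state.

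The consequence is a suggestion to modify before a full-scale trial, not a formal failure of the pilot. The defect is confined to half of one row.

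**What to change.** Before data are reviewed, amend the Participation cell of Table 4 in one of two ways.

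1. Keep 75% attending all 3 sessions as the only participation threshold, and report the share attending at least 2 sessions descriptively with a 95% confidence interval. The interval is informative even at the ceiling: 60 of 60 has an exact two-sided lower limit of 0.025^(1/60) = 94.0%.
2. Replace 100% with a level below 100%, chosen so that it is consistent with the assumed 25-30% loss after randomization and with the 85% retention row.

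Either way, state the denominator (all randomised couples, or couples who started the intervention) for each attendance proportion, and say how couples who separate before session 1 are counted. Under the second option, also say which element governs if they disagree.

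The cost is one table cell and a sentence on the denominator. The downside is that the stated attendance target looks less ambitious.

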5.3 General procedures for the FGDs: FGDs will be conducted in private rooms at community halls or at the HSRC Sweetwaters office. [name] will train research assistants on the study objectives, interview guide, and FGD methods using a decade’s worth of training materials from studies in SSA. Research assistants will conduct the FGDs in isiZulu or English using a structured guide. FGDs will elucidate ways to make the intervention more feasible and acceptable to the target population and to obtain feedback on the curriculum. We will ask: What are your overall impressions of this program? What aspects of the program will people like/dislike the most? What types of couples and drinkers will be most/least likely to participate? How can we improve the program to increase participation among couples? If this service was offered today, would you recommend it to couples? To assess how to implement the intervention in the future, FGDs with stakeholders will elicit feedback on strategies to increase uptake of the breathalyzers by local agencies. FGDs will be audio-recorded, transcribed, and translated to English.

5.4 Training. Given the skills required to deliver MI, we will hire certified HIV testing counselors with 2+ years of counselling and/or facilitation and community experience. Facilitators and the HSRC research manager will attend a multi-day didactic training workshop (in-person, at HSRC) with [name], following a curriculum based on workshops at the Motivational Interviewing Network of Trainers and [name] prior research on couples MI. The next few weeks will consist of role-plays, practice, coaching and feedback, including mock sessions with peers and pilot couples which will be recorded for [name]. A follow-up training session will be held to cover more advanced MI skills with [name]. This will be held online

Couple-Based Motivational Interviewing with Mobile Breathalyzers to Reduce Alcohol Use in South Africa

(Zoom) several weeks after the initial training and facilitators have had time to practice. To minimize intervention drift, facilitators will be required to conduct two additional mock counseling sessions per month in English, which will be video-recorded and used in monthly booster sessions with [name] (remotely on Zoom). The project manager at HSRC will also be trained by [name] on coaching techniques to help oversee the training and role playing in Zulu and provide feedback as needed.

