Before being cleared to interact with participants, facilitators will be required to demonstrate competency through three mock sessions in English.

We will also train a pair of interviewers to recruit couples and conduct assessment visits. Drs. [name] and [name] will lead additional training with staff, covering topics on couples counseling, the mobile breathalyzer technology, how to handle ethical issues with couples, health education around alcohol use and HIV, the intervention manuals and procedures, and professional conduct.

5.5 Supervision. Supervision of facilitators will occur as follows. Following each session, facilitators will listen to the audio-recording in Zulu and complete a self-assessment, identifying areas they did well, struggled with, or faced challenges with couples. The HSRC research manager or their peer facilitator will also listen to audio-recordings and complete an assessment form. Study investigators will meet with the research manager to discuss the self-assessments, and supervisor/peer assessments to assess competency and identify areas for further coaching. If budget allows, we will translate and transcribe a random set of MI sessions into English for [name] to provider further training.

[name] will provide monthly supervision to staff on intervention delivery. [name] will meet quarterly with [name] to provide strategic direction and support. PI [name] will take primary responsibility for the design, implementation and analysis of the qualitative data, working with the other co-Investigators.

5.6 Fidelity monitoring of intervention. After each session, facilitators will complete a checklist to ensure each section of the intervention was covered. Intervention sessions will be audio-recorded. The HSRC manager will listen to audio files of sessions and also complete a checklist for the sessions. Self-assessment forms described above will contain rating for key MI components (e.g., collaboration, respect, etc.). A separate space on the checklist and self-assessment forms will be provided for written comments. Completed forms will be discussed in regular Zoom calls with the team to discuss areas where further guidance is needed and to help problem-solve challenges.

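### Table 4 judges intervention fidelity by rater agreement alone, so fidelity can be reported as met when raters agree that delivery was poor

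*Combined protocol and SAP*

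**What the plan says.** Section 7.2 makes feasibility and acceptability (F&A) the primary objective. The primary analyses are descriptive statistics, "comparing each statistic (e.g., percent retained) to the threshold listed in Table 4". It adds that "Above-threshold findings will suggest a reasonable level of F&A", while falling short points to changes needed before a full-scale trial.

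The fidelity row of Table 4 covers arms 2 and 3. Its measure is "Expert ratings of quality of intervention using audio-recorded intervention sessions (checklists"; its threshold is ">80% inter-rater reliability". The row gives no minimum rating and names neither a reliability statistic nor the raters to be compared. The other thresholds on MI sessions concern attendance (all couples at 2 of 3 sessions, 75% at all 3) and length (at most 90 minutes).

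Sections 5.4 to 5.6 describe how delivery is supported and observed:

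- Section 5.4, before participant contact: "facilitators will be required to demonstrate competency through three mock sessions in English".
- Section 5.4, during the trial: "facilitators will be required to conduct two additional mock counseling sessions per month in English", used in monthly booster sessions.
- Section 5.5: facilitators complete a self-assessment after each session, and "The HSRC research manager or their peer facilitator will also listen to audio-recordings and complete an assessment form".
- Section 5.6: "facilitators will complete a checklist to ensure each section of the intervention was covered". The HSRC manager completes a checklist from the audio, the self-assessment forms rate key MI components, and completed forms are discussed on team calls.

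None of these passages states a pass mark.

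**The concern.** A fidelity criterion should answer whether the manualized sessions were delivered, and delivered well. Inter-rater reliability answers a different question: whether two people listening to the same session record the same thing. Two accurate raters who both record that half the content was skipped agree well, and by the rule in section 7.2 that counts in favour of feasibility.

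The consequence falls on how the pilot is read. Fidelity is part of the evidence on whether the intervention can go forward unchanged. It also helps in reading the exploratory comparisons H1 and H2 (section 7.3): without a delivery criterion, a weak signal is hard to attribute either to the intervention or to poor delivery of it.

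**Working it through.** The 80% figure is a chosen criterion, so there is no calculation in the plan to reproduce. The check asks what level of delivery a pass would imply.

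**Inputs.** From the documents: the threshold (80%) and the candidate raters (experts in Table 4; facilitator and HSRC manager in section 5.6; manager or peer in section 5.5). Assumed, because the documents give none: binary checklist items, independent rater errors, and the rater accuracies below. Let d be the true share of items delivered.

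**Case 1: two raters, each correct with probability a on every item.**

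- Percent agreement is Po = a² + (1 − a)². It does not contain d.
- At a = 0.95: 0.9025 + 0.0025 = 0.905. At a = 0.90: 0.81 + 0.01 = 0.82.
- Po exceeds 0.80 once a > (1 + √0.6)/2 = 0.887. The threshold then tests rater accuracy and nothing else.

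**Case 1 under kappa.** Kappa = (Po − Pe)/(1 − Pe), where Pe = r² + (1 − r)² and r = da + (1 − d)(1 − a).

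- At a = 0.95, kappa > 0.80 requires Pe < (0.905 − 0.80)/0.20 = 0.525.
- Since Pe = 0.5 + 2(r − 0.5)², this means |r − 0.5| < √0.0125 = 0.1118.
- Since r − 0.5 = 0.9(d − 0.5), it means |d − 0.5| < 0.124, so d lies between about 38% and 62%.
- At d = 95%, kappa is 0.448. With more accurate raters (a = 0.97), 20% delivery gives 0.829 (pass) and 95% delivery gives 0.591 (fail).

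**Case 2: two lenient raters, 98% correct on delivered items and 80% on undelivered ones.**

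- Po = 0.9608d + 0.68(1 − d), which reaches 0.80 at d = 0.12/0.2808 = 0.427.
- With the two error rates exchanged, Po = 0.68d + 0.9608(1 − d), and agreement falls as delivery improves.

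**Case 3: the facilitator ticks every item and the manager is 95% accurate.**

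- Po = 0.95d + 0.05(1 − d), which reaches 0.80 at d = 0.75/0.90 = 0.833.
- Kappa is 0 at every d, because one rater never varies and so Pe = Po.

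| Raters and statistic | d = 10% | d = 50% | d = 90% | Exceeds 80% when |
|---|---|---|---|---|
| Case 1, percent agreement | 90.5% | 90.5% | 90.5% | always |
| Case 1, kappa | 0.605 | 0.810 | 0.605 | d about 38% to 62% |
| Case 2, percent agreement | 70.8% | 82.0% | 93.3% | d > 42.7% |
| Case 2 exchanged, percent agreement | 93.3% | 82.0% | 70.8% | d < 57.3% |
| Case 3, percent agreement | 14% | 50% | 86% | d > 83.3% |
| Case 3, kappa | 0 | 0 | 0 | never |

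The exchanged crossing is (0.9608 − 0.80)/0.2808 = 0.573. The same wording can therefore demand high delivery, demand nothing, or reward poor delivery. Which of these applies depends on the raters and the statistic, and the plan specifies neither.

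**The case against.** The strongest defence is that section 5.6 itself pairs a facilitator checklist with a manager checklist. If facilitators over-report, percent agreement between the two does track delivery, and case 3 puts the implied floor at 83%. This stands as far as it goes, and a reader should not infer that the threshold carries no information about delivery under any reading. But the plan does not say that this is the pair compared, and Table 4 speaks of experts. Even then, agreement would be an indirect substitute for the manager's own coverage score.

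A reader might also take no floor to 83% as the range of delivery that the threshold implies. The documents do not support that. The range holds only for percent agreement under assumed accuracies, and under kappa the picture is different.

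A third tempting inference is that poor delivery would go unnoticed. It probably would not. The ratings would still be described, audio is reviewed, forms are discussed on team calls, exit interviews ask about MI content and format (section 5.14), and an investigator meeting considers final modifications. Table 4 also has a 75% satisfaction threshold. None of these is a fidelity pass mark, but together they limit the harm.

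Finally, the intervention manual, checklists and assessment forms are not reproduced in the protocol. The absence of a minimum is established for the protocol text only.

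**Conclusion.** The point holds. As written, the decision criterion for fidelity is a property of the ratings and not of delivery, so a fidelity pass can coincide with agreed poor delivery. Under kappa, near-complete delivery can also fail. This follows from the wording of Table 4 and section 7.2; the percentages above only illustrate it and rest on assumed rater accuracy, binary items and independent errors.

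Severity is modest. The row is one of ten descriptive indicators, section 7.2 says findings only suggest a conclusion, and no sample size, safety rule or hypothesis test depends on it. It is still worth fixing, because the reported result on fidelity would not mean what section 7.2 takes it to mean.

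**What to change.** Replace the threshold in the fidelity row with a minimum level on the audio-based ratings already planned, with values set and justified by the investigators:

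- **Content:** a minimum share of checklist items rated as delivered on the HSRC manager's checklist (section 5.6).
- **MI quality:** a minimum score on the manager or peer assessment form (section 5.5), if that form carries MI-quality items. The protocol does not list its items. If it has none, state that the pass mark covers content only, since a session can cover every item and still be poor MI.
- **Reporting:** give results separately for arms 2 and 3, and state which sessions are rated. At 30 couples per arm there are up to 2 × 30 × 3 = 180.
- **Raters:** say whether the HSRC manager is the expert meant in Table 4. Sections 5.4 and 5.5 give HSRC managers a part in coaching and supervising the facilitators, which should be noted as a limit on independence.
- **Agreement:** keep it as a separate check on measurement quality, naming the statistic and the pair of raters.

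The cost is an edit to one table row, using forms already planned. The downside is that a fidelity pass becomes harder to claim.
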